7.2.2.2 Adenoviral Eradication

Adenoviral eradication for an eye is defined as negative CC-IFA in that eye. CC-IFA for each eye will be conducted using conjunctival swab samples collected at each visit. See the Laboratory Manual for further details.

7.2.3 Safety

Safety assessments will be performed in both eyes.

7.2.3.1 Best Corrected Visual Acuity (BCVA)

The BCVA will be performed prior to slit lamp examination during the study as outlined in [Table 1](#).

The complete instructions for performing the BCVA are in the Study Operations Manual. Changes in VA will be assessed for clinical significance. Clinically significant changes should be recorded in the source and on the eCRF as an AE.

For subjects who are too young to use an ETDRS chart, use an age-appropriate measurement method in accordance with the AAP Policy Statement for Visual System Assessment in Infants, Children, and Young Adults by Pediatricians ([Donahue and Baker, 2016](#); [American Academy of Pediatrics, 2016](#); located in the Study Operations Manual). The policy statement recommends formal vision screening can begin at 3 years of age. VA measurements for children under the age of 3 will be done at the discretion of the investigator. If not done, child should be able to fixate on and follow a moving object. This is not a requirement in subjects <2 months of age since the ability does not develop until about 2 months of age. However, if an infant <2 months of age is able to fix and follow, it should be recorded. The enrollment of subjects <2 months of age will be based on subject qualifying all other eligibility criteria and investigator discretion.

VA is to be measured using the same method at all visits in the same subject.

7.2.3.2 Slit Lamp Biomicroscopy

Slit lamp biomicroscopy (or hand held slit lamp) will be performed during the study as outlined in [Table 1](#). Magnification of the slit lamp will be consistent with standard clinical practice. The subject will be seated.

Observations will be graded as Normal or Abnormal. Abnormal findings will be described, and clinically significant abnormalities should be recorded in the source and on the electronic CRF (eCRF) (in Medical History at Screening; any changes from the screening visit may be recorded as adverse events by the investigator). Please note the investigator may use his/her discretion to determine whether Not Clinically Significant (NCS) and disease progression should be considered AEs). The following will be examined at each visit:

- Lids
- Conjunctiva
- Cornea
- Anterior Chamber
- Iris
- Lens

For infants and young children, if the above exams cannot be performed with a slit lamp or a hand held slit lamp, an external examination is to be conducted in accordance with American Academy of Pediatrics (AAP) Policy Statement for Visual System Assessment in Infants, Children, and Young Adults by Pediatricians ([Donahue and Baker, 2016](#); [American Academy of Pediatrics, 2016](#); located in the Study Operations Manual). The examination of lens in these subjects should be conducted at Visit 1 and Visit 5 (or ET visit) and graded based on the external examination and red reflex exam (Section [7.2.3.3](#)).

All other structures listed above will be examined and graded at all visits based on the external examination. Observations will be graded as Normal or Abnormal. Abnormal findings will be described.

7.2.3.3 Non-dilated/ Dilated Fundus Examination

Fundus examination must be conducted after BCVA, Slit Lamp Biomicroscopy and conjunctival swab for adenoviral and bacterial culture has been collected.

A non-dilated fundus examination will be performed in all subjects with the exception of infants and uncooperative small children during the study as outlined in [Table 1](#).

Observations will be graded as Normal or Abnormal. Abnormal findings will be described.

The following will be examined:

- Vitreous
- Optic Nerve
- Macula

Clinically significant changes should be recorded in the source and on the eCRF as an AE.

If a non-dilated fundus exam is attempted and is not feasible, dilated fundus exam should be conducted. The test should be conducted the same way (either dilated or non-dilated) at both Visit 1 and Visit 5 (or ET).

For infants and small children in whom a fundus examination cannot be done, a red reflex exam will be conducted in accordance with AAP Policy Statement for Visual System Assessment in Infants, Children, and Young Adults by Pediatricians ([Donahue and Baker, 2016](#); [American Academy of Pediatrics, 2016](#); located in the Study Operations Manual). Observations will be graded as Normal or Abnormal. Abnormal findings will be described. The red reflex should be normal (present and symmetrical for both eyes) at the screening/ baseline visit.

7.2.3.4 Adverse Event Collection

At each study visit, subjects will be questioned in a general way to ascertain if AEs have occurred since the previous visit (eg, “Have you had any health problems since your last visit?”). Adverse events are collected from the time informed consent is signed. (Please refer to [Section 8](#), Adverse and Serious Adverse Events Assessment.) Any AE that occurs after the first dose of investigational product instillation will be considered a TEAE.

Adverse events may also be determined by the investigator during study examinations as mentioned in previous sections.

7.2.3.5 Microbiology Laboratory Evaluations

All laboratory assays will be performed according to the laboratory’s normal procedures.

All bioanalytical assays for the study will be validated following FDA/ICH guidelines, based on the method's intended use. The lab will only receive sample ID numbers and collection dates, the lab results will then be transferred to the central lab for data analysis. The lab will not receive any information on subject treatment assignment.

The following laboratory assessments will be performed:

- Cell Culture Immunofluorescence Assay (CC-IFA): This test will be performed on samples collected at all visits to determine the presence of adenovirus.
- qPCR: This test will be performed on all CC-IFA positive samples at all visits to determine viral count.
- Adenoviral serotyping: This test will be done at baseline only to determine what serotypes of adenovirus are present.
- qPCR: This test will be performed on samples for qualitative detection of HSV at baseline (Visit 1).

One swab sample from each eye will be taken from inferior conjunctival cul-de-sac at all study visits for adenoviral testing. For neonates and infants <2 months of age, PCR testing for qualitative detection of chlamydia and gonorrhea at baseline will also be conducted using the baseline visit sample.

7.2.3.6 Pregnancy Test

A urine pregnancy test is performed on all females of childbearing potential at Visit 1 and Visit 5, or if pregnancy is suspected. Urine pregnancy test kits will be provided by the sponsor and read on site by qualified site personnel.

7.2.3.7 Health-related Quality of Life Assessments

Ocular discomfort associated with conjunctivitis symptoms will be assessed through the Ocular Discomfort Scale. The Ocular Discomfort Scale is composed of three items: pain, itching, and foreign body sensation. All items will be evaluated using a 0-10 scale. A separate scale will be administered for children less than 8 years of age (binary ocular discomfort). Please see the Study Operations Manual for a detailed description of this assessment.

8. ADVERSE AND SERIOUS ADVERSE EVENTS ASSESSMENT

8.1 Definition of Adverse Events, Period of Observation, Recording of Adverse Events

An AE is any untoward medical occurrence in a clinical investigation subject administered a pharmaceutical product and that does not necessarily have a causal relationship with this treatment. An AE can therefore be any unfavorable and unintended sign (including an abnormal laboratory finding), symptom, or disease temporally associated with the use of a medicinal (investigational) product, whether or not related to the medicinal (investigational) product (ICH Guidance E2A 1995).

All AEs are collected from the time the informed consent is signed until the defined follow-up period stated in Section 7.1.3. This includes events occurring during the screening phase of the study, regardless of whether or not investigational product is administered. Where possible, a diagnosis rather than a list of symptoms should be recorded. If a diagnosis has not been made, then each symptom should be listed individually. All AEs should be captured on the appropriate AE pages in the CRF and in source documents. In addition to untoward AEs, unexpected benefits outside the investigational product indication should also be captured on the AE CRF.

All AEs must be followed to closure (the subject's health has returned to his/her baseline status or all variables have returned to normal), regardless of whether the subject is still participating in the study. Closure indicates that an outcome is reached, stabilization achieved (the investigator does not expect any further improvement or worsening of the event), or the event is otherwise explained. When appropriate, medical tests and examinations are performed so that resolution of event(s) can be documented.

8.1.1 Severity Categorization

The severity of AEs must be recorded during the course of the event including the start and stop dates for each change in severity. An event that changes in severity should be captured as a new event. Worsening of pre-treatment events, after initiation of investigational product, must be recorded as new AEs (for example, if a subject experiences mild intermittent dyspepsia prior to dosing of investigational product, but the dyspepsia becomes severe and more frequent after first dose of investigational product has been administered, a new AE of severe dyspepsia [with the appropriate date of onset] is recorded on the appropriate CRF).

The medical assessment of severity is determined by using the following definitions:

- Mild:** A type of AE that is usually transient and may require only minimal treatment or therapeutic intervention. The event does not generally interfere with usual activities of daily living.
- Moderate:** A type of AE that is usually alleviated with specific therapeutic intervention. The event interferes with usual activities of daily living, causing discomfort but poses no significant or permanent risk of harm to the research subject.
- Severe:** A type of AE that interrupts usual activities of daily living, or significantly affects clinical status, or may require intensive therapeutic intervention.

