9.8.5 Exploratory Efficacy Endpoints

9.9 Safety Analyses

Safety data will be presented for the Safety Population by treatment group and overall.

Safety data collected at baseline (Visit 1 / Day 1) will be used as the baseline value for safety analysis.

Adverse events, including those suggestive of any local tolerability issues, will be coded using the Medical Dictionary for Regulatory Activities. The number of subjects and percentage with a treatment-emergent adverse event (TEAE) as well as the number of TEAEs will be calculated overall, by SOC, by preferred term, and by treatment group and overall. Treatment-emergent adverse events will be further summarized by severity and relationship to investigational product. Adverse events related to investigational product, AEs leading to withdrawal, SAEs, and deaths will be similarly summarized and listed.

Generally, TEAEs will be presented separated by whether or not the AE was an ocular or non-ocular AE.

The following safety endpoints will be descriptively summarized by treatment group and overall at each applicable visit:

- Best Corrected Visual Acuity (BCVA)
- Slit Lamp Biomicroscopy
 - Lids
 - Conjunctiva
 - Cornea
 - Anterior Chamber
 - Iris
 - Lens
- Non-dilated/ Dilated Fundus Examination
 - Vitreous
 - Optic Nerve
 - Macula
- Urine Pregnancy Testing (for females of childbearing potential)

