11.1 Adverse Events

AEs will be coded using MedDRA version 19.1. Any AE that occurs after the first dose of investigational product instillation will be considered a treatment- emergent adverse event (TEAE).

An overall summary of the number of subjects with TEAEs will be presented, including the number and percentage of subjects with any TEAEs, ocular TEAEs, non-ocular TEAEs, TEAEs leading to death, serious TEAEs, TEAEs related to investigational product and TEAEs leading to discontinuation of investigational product as well as the total number of events in each category.

The number and percentage of subjects reporting TEAEs in each treatment group and across all subjects will be tabulated by System Organ Class (SOC) and Preferred Term (PT) as well as by SOC, PT, and maximum severity. TEAEs considered related to investigational product will also be summarized by SOC and PT. If more than 1 AE occurs with the same SOC/PT for the same subject, then the subject will be counted only once for that SOC/PT using the most severe and most related occurrence for the summarization by severity and by relationship to investigational product, respectively. The incidence of common TEAEs ($\geq 5\%$ of subjects in any treatment group) will also be summarized by SOC and PT. Serious TEAEs, TEAEs leading to discontinuation of investigational product and TEAEs leading to death, will be summarized by SOC, PT and treatment group and across all subjects. The number and percentage of subjects reporting local tolerability TEAEs (overall, related to IP and not related to IP) in each treatment group and across all subjects will also be tabulated by SOC and PT. PTs that are considered to be local tolerability AEs will be provided by global drug safety (GDS) before database lock. Separate tables will be generated for ocular TEAEs and non-ocular TEAEs. For all above tables, ocular TEAEs will be summarized at subject level and also by study eye, fellow eye and both eyes.

Listings of all TEAEs will be provided by subject.

Pre-treatment events (captured on the AE form that occurred prior to the first dose of investigational product) will be listed by subject but not tabulated.

Imputed dates, severity and relationship (see Section 18.7, 18.8 and 18.9 respectively for imputation rules) to investigational product will be marked in the listings.

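### TEAE event totals will count severity changes as separate events, because no rule joins the records of one episode

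*Protocol*

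**What the plan says.** Protocol 8.1.1 sets the recording rule: "An event that changes in severity should be captured as a new event". Severity is to be recorded "including the start and stop dates for each change in severity", so each severity segment carries its own dates. The next sentence of 8.1.1 deals with events already present before dosing: "Worsening of pre-treatment events, after initiation of investigational product, must be recorded as new AEs".

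The definition of treatment-emergent rests on timing alone. Protocol 7.2.3.4 states: "Any AE that occurs after the first dose of investigational product instillation will be considered a TEAE". SAP 11.1 uses the same words. Neither compares a post-dose record with the grade before dosing.

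For reporting, SAP 11.1 gives an overall summary of subjects with TEAEs (any, ocular, non-ocular, leading to death, serious, related, leading to discontinuation) "as well as the total number of events in each category". This is Table 14.3.1.1 in SAP 21. Protocol 9.9 promises more: numbers and percentages of subjects "as well as the number of TEAEs will be calculated overall, by SOC, by preferred term" and by treatment group. SAP 11.1 describes the SOC and PT tables as numbers and percentages of subjects only.

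The one de-duplication rule in SAP 11.1 works on subjects: a subject with several AEs in the same SOC/PT is counted once, at the most severe and most related occurrence. SAP 18 contains no rule that links records of one episode.

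**The concern.** Collecting one record per severity grade is a sound way to capture data. The gap is in the counting. If each segment is a new event, and every event after the first dose is a TEAE, then an episode that eases from moderate to mild adds two to the event total, and the second entry records nothing but improvement. Easing will often be captured, because Protocol 8.1 asks for every AE to be followed to closure.

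Under SAP 17 the report after early termination will be full on safety and abbreviated on efficacy, with no hypothesis tests. Readers will rely on descriptive safety tables. A total labelled as events would partly measure how often severity was re-graded.

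**Working it through.** The documents state no AE count and no rate of severity change, so there is no figure of the plan's own to reproduce. The check traces the rules and counts.

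**Inputs**

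- A new event at each severity change, direction not stated (Protocol 8.1.1).
- Separate start and stop dates for each change (Protocol 8.1.1).
- TEAE defined by timing only (Protocol 7.2.3.4, SAP 11.1).
- Event totals reported (SAP 11.1 overall summary; also Protocol 9.9).
- De-duplication of subjects only (SAP 11.1).
- AEs collected from consent, which can be on Day -1 or Day 1 (Protocol 8.1, Table 1).

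**Formula**

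An episode that starts after dosing and has k severity changes gives 1 + k TEAE records. For N such episodes with a mean of c changes each, the event total is N × (1 + c). The inflation factor relative to the number of episodes is therefore 1 + c.

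**Single episodes**

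| Course of one episode | TEAE events as written | Subjects counted for that PT as written | Events if episodes are linked and TEAE means onset or worsening |
|---|---|---|---|
| Post-dose, mild throughout | 1 | 1 | 1 |
| Post-dose, moderate then mild | 2 | 1 | 1 |
| Post-dose, mild, moderate, mild | 3 | 1 | 1 |
| Pre-dose mild, post-dose moderate | 1 | 1 | 1 |
| Pre-dose moderate, post-dose mild | 1 on a literal reading | 1 on a literal reading | 0 |

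**Totals, for assumed values of c**

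- c = 0: 1 + 0 = 1.0
- c = 0.1: 1 + 0.1 = 1.1
- c = 0.3: 1 + 0.3 = 1.3
- c = 0.5: 1 + 0.5 = 1.5
- c = 0.6 (for example, 30% of episodes changing grade twice, 0.30 × 2): 1 + 0.6 = 1.6

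**What is not affected**

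In the first three rows the subject count stays at 1 whatever k is. The once-per-SOC/PT rule keeps subject incidence correct, and the maximum-severity table takes the worst segment. Only the last row reaches a subject count, and it requires an AE that began between consent and the first drop.

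**The case against.** **Reach.** In the SAP, event totals are described only for the overall summary. The SOC/PT, severity, related, serious, discontinuation and local-tolerability tables count subjects. This stands. A reader might infer that TEAE incidence, or the safety report as a whole, is inflated. The documents do not support that for events that begin after dosing. Protocol 9.9 does promise event numbers by SOC and PT, and if those were produced the same problem would apply to them.

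**Improvement of a pre-dose event.** The sentence after the recording rule names only worsening of pre-treatment events. It would be largely redundant if the general rule already covered such events in both directions. Improvement is also hard to call an adverse event, and the SAP's rule on missing AE dates (18.7) implies that the CRF records whether an event preceded the first dose. Against this, the general sentence is not limited by direction, and nothing says that a record made for a severity change keeps its pre-dose status. The text is ambiguous. The window is also short, and Protocol 8.1.4 keeps expected disease symptoms out of the AE data. This route can be mentioned but cannot carry the point.

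**Size and direction.** A reader might also infer a large inflation, such as 60%, or a bias between arms because only SHP640 contains a steroid. Neither is shown. The 1.6 factor is an assumption, and no rate of severity change is given overall or by arm. If the mean number of changes is the same in all arms, every total is scaled by the same factor.

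**Versions and other documents.** SAP 1 refers to protocol amendment 4.0 of April 5, 2019, while Protocol Appendix 1 ends at Amendment 3. AE follow-up text in the footnotes to SAP Table 1 is absent from the protocol's table, so some AE wording appears to have changed. Table specifications are held separately and might contain a counting rule. This lowers confidence; it does not fill the gap in the SAP text.

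**Merging.** Joining records is not trivial. SAP 18.7 leaves incomplete stop dates unimputed, segments can differ in relatedness or seriousness, and merging across the first dose could hide true worsening. These objections are sound, and the fix has to deal with them.

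**Conclusion.** The point holds for event totals. As written, each post-dose episode contributes one TEAE plus one more for every severity change, improvements included, and no SAP rule corrects this. The totals are 1 + c times the number of episodes: 1.1 to 1.6 for assumed c of 0.1 to 0.6, and exact if no grade changes. The true value cannot be derived from the documents.

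The certain reach is the event totals in the overall TEAE summary, plus any event counts by SOC and PT produced to meet Protocol 9.9. Subject counts and maximum-severity tables are sound for events that begin after dosing. A pre-dose AE counted as a TEAE only because it improved is a rare case and a disputable reading.

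The conclusion assumes that sites follow 8.1.1 literally, that 8.1.1 is unchanged in amendment 4.0, and that the separate table specifications contain no linking rule. Confidence is moderate for those reasons.

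**What to change.** First check that 8.1.1 reads the same in protocol amendment 4.0. Then amend SAP 11.1:

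1. **TEAE definition.** An AE that starts after the first dose, or that worsens after the first dose relative to its pre-dose grade. Onset should mean onset of the episode, so that a record created only because a pre-dose event eased does not qualify.
2. **Event totals.** Among records that meet (1), count contiguous records of the same subject, preferred term and eye as one event, at maximum severity. Count that event as related, serious or leading to discontinuation if any of its segments is. Restricting the merge to records that meet (1) keeps a pre-dose event that truly worsened as a TEAE.
3. **Incomplete dates.** Where dates are too incomplete to show that records are contiguous, leave them separate.
4. **Listings.** Keep every record.

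At minimum, label the totals as numbers of AE records rather than events.

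The cost is SAP wording and a small derivation from dates and grades that 8.1.1 already collects. No new data are needed. Event totals will come out somewhat lower; subject counts will not change, apart from any rare pre-dose case that only improved.

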8.1.2 Relationship Categorization

A physician/investigator must make the assessment of relationship to investigational product for each AE. The investigator should decide whether, in his or her medical judgment, there is a reasonable possibility that the event may have been caused by the investigational product. If there is no valid reason for suggesting a relationship, then the AE should be classified as “not related.” Otherwise, if there is any valid reason, even if undetermined or untested, for suspecting a possible cause-and-effect relationship between the investigational product and the occurrence of the AE, then the AE should be considered “related.” The causality assessment must be documented in the source document.

The following additional guidance may be helpful:

| Term | Relationship Definition |
|-------------|---|
| Related | The temporal relationship between the event and the administration of the investigational product is compelling and/or follows a known or suspected response pattern to that product, and the event cannot be explained by the subject’s medical condition, other therapies, or accident. |
| Not Related | The event can be readily explained by other factors such as the subject’s underlying medical condition, concomitant therapy, or accident and no plausible temporal or biologic relationship exists between the investigational product and the event. |

